9.0 STATISTICAL CONSIDERATIONS

The full details of the trial planning computations and planned analyses are contained in a separate Statistical Analysis Plan. Key features are summarized below. This study will be monitored by an independent Data Monitoring Committee and the charter for this committee is based on FDA guidance.

9.1 Study Design

This 1,200 subject (approximately) study is a randomized, double-blind, placebo-controlled, three-arm clinical trial. The primary endpoint is survival time or time to the most recent knowledge of “known to be alive” (censored time). Zero time is defined as the date of randomization.

Subjects will be randomly partitioned with equal probability into one of three double-blinded arms, an investigational arm where the intended intervention is vaccine (PROSTVAC-V/F) plus GM-CSF (Arm V+G), an investigational arm where the intended intervention is vaccine (PROSTVAC-V/F) with placebo GM-CSF (Arm V), and a control arm where the intended intervention is an empty fowlpox vector and placebo GM-CSF (Arm P).

(Arm V+G)	PROSTVAC-V/F plus GM-CSF
(Arm V)	PROSTVAC-V/F plus GM-CSF placebo
(Arm P)	Double placebo (empty fowlpox vector / plus GM-CSF placebo).

The association of intervention to arm will be hidden from clinical personnel and subjects by using a coded identifier for each intervention preparation to be administered. Specifically, the arm designators shown above (V+G, V, and P) are for statistical purposes.

9.2 Randomization

Block randomization will be used to randomly assign subjects in a 1:1:1 manner. Randomization will be stratified by PSA (equal and above, or below 50 ng/mL), and LDH (equal and above, or below 200 u/L). Subjects will be randomized through IVRS/IWRS.

9.3 Analysis Sets

Three analysis sets are defined for this trial. The Intent-to-Treat set (ITT) includes all subjects who are randomized. The full analysis set (FAS) includes all subjects initiating study intervention. The safety analysis set includes all subjects initiating study intervention. The FAS and safety analysis set are the same.

All efficacy analyses will be performed on the ITT set and the FAS. Subjects will be analyzed and summarized based on the arm into which they were randomized. Efficacy analysis performed on the ITT analysis set will be considered to be the primary indicator of efficacy. Analysis performed on the FAS will be considered to be supportive.

All safety analyses will be performed on the Safety set.

9.4 Primary Efficacy Analysis

Two main overall comparisons of survival time are planned: A comparison between Arm V+G and Arm P, and a comparison between Arm V and Arm P. Thus two separate tests will be assessed, and success for the trial is defined as meeting statistical criterion for either of the following comparisons.

- Superiority of Arm V+G over Arm P for all subjects randomized to these arms.
- Superiority of Arm V over Arm P for all subjects randomized to these arms.

The overall type one error probability (alpha error) for the whole study is designed as a one sided $P=0.025$. There are two main overall comparisons, which therefore necessitate a type one error probability to 0.0125 for each comparison based on using a Bonferroni correction.

The primary analysis methodology will be the stratified log rank test.

9.5 Trial Size

The Arm P reference data for planning this trial is specified as a median survival of 22 months based on the placebo arm of Dendreon D9902B. Based on exponential assumptions the corresponding hazard rate is 0.3781 and the corresponding three-year survival is 32.2%.

The hazard ratio to be used in the specific alternative hypotheses used to compute trial size is specified to be 0.68 for the main comparisons, that is, a 32% smaller hazard rate in Arm V+G or Arm V as compared to Arm P. This hazard ratio is based on hazard ratio estimates from the previously completed randomized Phase 2 trial with an allowance that the Phase 2 trial likely provides an over-optimistic estimate of the true hazard ratio. The hazard ratio estimate from the Phase 2 trial was 0.56, and was approximately 0.5 when delayed effect is taken into account (depending on the characterization of the delayed effect).

Simulations project that 534 events for each between-arm comparison are required for a minimum of 85% power to detect a 32% lower hazard rate. These calculations have taken in to consideration a delayed treatment effect (as found in the randomized phase 2 study). If there is less delayed effect the power will be greater. The projection for the time to realize the required number of deaths for final analysis is 4.6 years following the start of accrual.

9.6 Secondary Efficacy Endpoint

The secondary efficacy endpoint is a binary assessment for Alive without Event (AWE) at six months (or early termination). The event is any of the following on or before six months: radiological progression, pain progression, chemotherapy initiation, or death. Subjects without an event prior to six months will have an evaluation for event at six months. Subjects without event who are not evaluated at six months (or early termination) will be assumed to have had an event. Thus, each subject will be defined as AWE =

1 if the subject is alive and free of event at six months (or early termination) and AWE = 0 otherwise. AWE will have a realization for every subject and therefore is amendable to an intent-to-treat analysis.

The same two comparisons as done for survival will be done for AWE, using the same significance levels. For each comparison the proportions of subjects in each arm for which AWE = 1 will be compared. The probability is 90% or greater that this statistical test will be significant if the true proportion difference is 0.1375 or greater. The critical difference is 0.092 if the control arm proportion is 0.5.

9.7 Safety Analyses

The primary safety analysis set will be all subjects initiating study intervention. The primary focus will be a between-arm comparison of the frequency and severity of safety events without attribution. Supporting analyses will be comparisons of subjects according to intervention received and attribution.

Adverse events will be summarized and tabulated by severity and by relationship to study intervention (attribution). The original terms used by investigators to identify AEs in the CRFs will be translated into preferred terms using current MedDRA Thesaurus. The AEs will be grouped by MedDRA preferred terms into frequency tables according to body system. The number and percentage of subjects experiencing adverse events will be tabulated by body system/preferred term and treatment. When an AE occurs more than once, the maximum severity and causality will be listed only once. Additionally, SAEs and AEs that are possibly or probably related to study intervention will be summarized separately. Data listings of all AEs will be provided by individual subject.

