5.2.2 Trial Stopping Rules

In the event of a death definitely related to study drug within 24 hours of vaccination or ≥ 3 definitely related SAEs (per 20 patients) at any time after receiving study drug during the treatment period, dosing will halt immediately and the DMC will be consulted. All data will be reviewed prior to any further dosing, and dosing will not continue until the DMC agrees that it is safe to continue. At the discretion of the DMC, the FDA or other Health Regulatory Agencies may be consulted. The decision to permanently halt the trial may only be made by BNI Executive Committee.

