8.5 Assessment of Relationship to Study Drug (Causality)

Investigators are required to assess the causal relationship (i.e., whether there is reasonable possibility that the study drug caused the event) using the following definitions:

Unrelated: Another cause of the adverse event is more plausible; a temporal sequence cannot be established with the onset of the adverse event and administration of the investigational product; or, a causal relationship is considered biologically implausible.

Possibly Related: There is clinically plausible time sequence between onset of the adverse event and administration of the investigational product, but the adverse event could also be attributed to concurrent or underlying disease, or the use of other drugs or procedures. Possibly related should be used when the investigational product is one of several biologically plausible adverse event causes.

Definitely Related: The adverse event is clearly related to use of the investigational product.

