8.12 Adverse Event Reporting Period

The AE reporting period for this study begins with signing of the informed consent and ends 28 days following administration of the last dose of study medication. If an SAE is present at the EOT Visit, the SAE (and associated AEs and concomitant medications) should be followed to resolution or until the Investigator assesses the subject as stable, or the subject is lost to follow-up or withdraws consent. Resolution/stable means the subject has returned to baseline state of health or the Investigator does not expect any further improvement or worsening of the event.

New SAEs will be collected until 28 days following administration of the last dose of study medication . If an SAE comes to the attention of the investigator after the end of the study, information regarding the SAE should be collected and reported only if assessed as possibly or definitely related by the investigator.

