8.15 Treatment and Follow-up of Adverse Events or Serious Adverse Events

From the time the subject signs informed consent until 28 days after the last vaccination, all untoward medical events (as defined in [Section 8.2](#) and exceptions as noted in [Section 8.4](#)) will be documented as (S)AEs through the Treatment phase of the study or through the last visit of the Treatment phase of the study for subjects who withdraw early.

All (S)AEs assessed as not related to study vaccine will be followed as clinically indicated until resolved, stabilized, or if non-resolving, until 28 days after the last vaccination, whichever comes first. If a clear explanation is established, it should be recorded on the CRF.

If an SAE is assessed as possibly or definitely related to study vaccine, it must be followed until either the event has resolved, stabilized, or is deemed to be non-resolvable by the investigator.

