9.1.1. Incidence of Adverse Events

The frequency and percentage of subjects with TEAEs will be tabulated for overall incidence by system organ class (SOC) and PT for primary period TEAEs, booster period TEAEs and overall.

TEAEs will also be summarized by treatment arm and overall for the highest CTCAE grade and highest relationship to study treatment within each subject. Related TEAEs, serious TEAEs, related serious TEAEs, and TEAEs resulting in study product discontinuation will be similarly summarized. Additionally, the incidence of TEAEs and related TEAEs will be summarized by PT in descending order of total frequency. The incidence of TEAEs coded as injection site reactions will be summarized by type of injection (primary or booster) and by arm.

At each level of summarization, a subject will be counted only once for each AE he/she experiences within that level.

Data listings of all AEs and SAEs will be provided. Adverse events presented in the listings will be those recorded from the first dose date through the end of follow-up.

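### Protocol 9.7 selects related events by a causality level that the Section 8.5 scale does not contain, so read literally one supplementary safety summary omits Definitely Related events (minor).

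*Protocol*

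**What the plan says.** Protocol 8.5 requires investigators to rate causality on three defined levels:

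- "Unrelated: Another cause of the adverse event is more plausible", with further conditions.
- "Possibly Related: There is clinically plausible time sequence between onset of the adverse event and administration of the investigational product", with the proviso that other causes could also explain the event.
- "Definitely Related: The adverse event is clearly related to use of the investigational product".

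Protocol 9.7 makes the between-arm comparison of safety events, disregarding attribution, the primary focus. It then calls for tabulation by severity and by relationship to study intervention. A further, separate summary is added: "Additionally, SAEs and AEs that are possibly or probably related to study intervention will be summarized separately". Listings of all AEs by subject complete the section.

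SAP 9.1.1 summarizes treatment-emergent events by highest grade and highest relationship within subject, and adds: "Related TEAEs, serious TEAEs, related serious TEAEs, and TEAEs resulting in study product discontinuation will be similarly summarized". It does not say which of the 8.5 levels make an event related. It also plans a table of injection-site reactions by type of injection and arm.

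Elsewhere the protocol keeps to its own scale. An SAE that becomes known after the end of the study is to be "reported only if assessed as possibly or definitely related by the investigator" (8.12). The follow-up duty in 8.15 begins "If an SAE is assessed as possibly or definitely related to study vaccine".

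**The concern.** Section 9.7 names two levels for the related-event summary. One of them does not exist on the scale, and the level expressing the greatest certainty of a causal link is missing. A programmer who follows the sentence as written would produce a related-event table without any event that the investigator considered clearly caused by the product.

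Related-AE and related-SAE tables are a usual place for a reader to look for attributable toxicity, and the safety objective in Protocol 3.1.3 is to characterize the type and number of AEs against placebo. A team that silently reads the sentence sensibly would get the right table, but would depart from the protocol text with no written derivation in the SAP to support it. What is at stake is the content and traceability of one supporting safety output. No efficacy result, sample size, error rate or data collection depends on it.

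**Working it through.** No formula or stated figure is involved. The check compares the levels that can be recorded with the levels that are selected.

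| Place | Levels named |
|---|---|
| Protocol 8.5 (scale) | Unrelated, Possibly, Definitely |
| Protocol 9.7 (separate summary) | Possibly, Probably |
| Protocol 8.12 (SAEs learned of after study end) | Possibly, Definitely |
| Protocol 8.15 (follow-up of SAEs) | Possibly, Definitely |
| SAP 9.1.1 (related-event tables) | none stated |

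**Step 1: apply the 9.7 rule to the 8.5 scale.** {Possibly, Probably} ∩ {Unrelated, Possibly, Definitely} = {Possibly}. The *probably* category is always empty, and *definitely* is not selected.

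**Step 2: allow for the two ways of parsing the sentence.** The qualifier in 9.7 may apply to SAEs and AEs alike (reading A). It may also apply to AEs only, so that all SAEs are summarized together with the qualifying AEs (reading B). Three hypothetical records show the difference:

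| Record | Reading A | Reading B |
|---|---|---|
| Non-serious induration at the injection site, rated Definitely | omitted | omitted |
| Non-serious myalgia, rated Possibly | included | included |
| Serious anaphylaxis, rated Definitely | omitted | included |

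Non-serious events rated Definitely are omitted either way. Serious ones are omitted only under reading A.

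**Step 3: look for the same events in other planned outputs.**

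- The by-relationship tabulation in Protocol 9.7 is not limited to particular levels, so it includes Definitely Related events.
- The SAP 9.1.1 summary by highest relationship includes them.
- The SAP 9.1.1 table of serious events does not depend on causality, so it includes the anaphylaxis record.
- The SAP 9.1.1 injection-site table does not depend on causality either, so it includes the induration record if it is coded as an injection-site reaction.
- The AE listings include all of these records.

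**Step 4: ask what was meant.** Both other places in the protocol that pair two levels for related SAEs, 8.12 and 8.15, use possibly and definitely. No passage gives a reason to leave Definitely Related events out of a related-event table. The most economical explanation is one wrong word in 9.7.

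**The case against.** The strongest reply is that nobody would be misled. Two of the three level names in 8.5 contain the word related, so the related tables in SAP 9.1.1 are naturally read as covering both. Protocol 9.0 leaves the full details of the analyses to the SAP, and the SAP has no filter that excludes the definite level. The events are visible in several other outputs, and 9.7 itself treats comparisons by attribution as supporting.

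Most of this stands, and it limits the point to one summary. It does not remove the point: 9.7 is the only sentence in either document that names levels for a related-event summary, it cannot be carried out as written on the collected data, and the SAP does not define the term.

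A reader might infer three stronger things, none of which the documents support:

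- **That the omission makes the vaccine arms look safer than placebo.** Protocol 1.3 describes skin reactions to the empty fowlpox vector as overlapping with those to PROSTVAC-V and hard to tell apart from them, and the trial is double-blind. Reactions in Arm P could also be rated Definitely and drop out. No direction of bias is shown.
- **That a known share of men would lose an event from the table.** Protocol 1.6 expects injection-site reactions in at least 50% of recipients, but neither document says how many would be rated Definitely. Sections 8.3.1 and 8.4 also leave some doubt about whether every expected reaction reaches the AE form. Any percentage would rest on an unsourced assumption.
- **That safety monitoring is affected.** The stopping rule in Protocol 5.2.2 begins "In the event of a death definitely related to study drug within 24 hours of vaccination", and it and the dose-limiting toxicity definition in 5.2.1 turn on the investigator's rating of each event. They do not draw on the 9.7 summary.

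**Conclusion.** The mismatch is real and lies in current text. Taken literally, the separate related-event summary in Protocol 9.7 keeps only Possibly Related events and omits every Definitely Related AE; Definitely Related SAEs go too if the qualifier covers them. The SAP does not resolve this, because it leaves related undefined. The protocol's own usage in 8.12 and 8.15 points to a wording slip and not to an intended exclusion.

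The size is small. One supplementary output is affected, the events remain visible in the other tables and the listings, and the primary safety comparison, which disregards attribution, is untouched. The conclusion assumes only that causality is recorded on the 8.5 scale and that 9.7 is applied as written. Severity: minor, a consistency correction worth making before the safety tables are programmed.

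**What to change.** In Protocol 9.7, change the word *probably* to *definitely*, so that the sentence selects the same two levels as 8.12 and 8.15. In the same edit, make clear whether the qualifier applies to SAEs as well as AEs.

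In SAP 9.1.1, add one sentence: an event is related if it is rated Possibly Related or Definitely Related on the scale in Protocol 8.5.

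The cost is one word and a small clarification in the protocol, and one sentence in the SAP. No data collection, form or other planned table changes. If a protocol amendment is not otherwise due, the SAP sentence alone gives the programmers a usable derivation, and the protocol wording can be corrected at the next amendment.

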9.8 Interim Analyses

An interim analysis plan (IAP) is included in the SAP for this study. Interim analyses are executed by [REDACTED] a Contract Research Organization that acts as the independent statistician and assessed by the DMC as described in the DMC Charter. At each interim analysis, both unblinded (closed) and blinded (open) interim analysis reports will be provided to the DMC, while the sponsor will only receive an open (blinded) report unless one of the criteria is met. Even in this case, the DMC will use its discretion regarding the communications of results to the sponsor, with patient safety balanced against benefit being the primary concern.

The IAP was designed to detect early evidence of both efficacy and futility. Interim analyses for the two comparisons of overall survival described in Section 9.4 are to be executed at 40%, 60%, and 80% of information times, corresponding to 214, 321, and 427 deaths per comparison. The final analysis will be completed when 534 deaths per comparison have occurred. To maintain an overall one-sided type I error probability of 0.0125 per comparison, the one-sided significance criteria using one-sided O'Brien-Flemming boundaries for early detection of efficacy analyses are 0.000135, 0.00147, 0.00501, respectively, with the adjusted final analysis to use 0.01063. The significance level to be used for detection of futility at each interim analysis is 0.00001. This futility significance level was chosen in order

**Protocol BNIT-PRV-301; Amendment 7
PROSTVAC-V/F**

to provide a balance between the sought for estimated probability of detecting futility and protecting against falsely detecting futility.

10.0 STUDY ADMINISTRATION AND INVESTIGATOR OBLIGATIONS

10.1 Regulatory and Ethical Compliance

This clinical study was designed and will be implemented in accordance with the protocol, the ICH Harmonized Tripartite Guidelines for Good Clinical Practices, with applicable local regulations (including US Code of Federal Regulations Title 21 and European Directive 2001/20/EC), and with the ethical principles laid down in the Declaration of Helsinki.

10.2 Institutional Review Board (IRB), Research Ethics Board (REB), and Independent Ethics Committee (IEC) Approval

The Investigator will submit this protocol, the informed consent, Investigator Brochure, and any other relevant supporting information (e.g., all advertising materials or materials given to the subject during the study) to the appropriate IRB/REB/IEC for review and approval before study initiation. Amendments to the protocol and informed consent form must also be approved by the IRB/REB/IEC before the implementation of changes in this study.

The Investigator is responsible for providing the IRB/REB/IEC with any required information before or during the study, such as SAE expedited reports or study progress reports.

The IRB/REB/IEC must comply with current United States (US) regulations (§21 CFR 56) (unless a waiver to the IRB requirements of the 1572 has been obtained) as well as country-specific national regulations and/or local laws.

The following documents must be provided to BNI or its authorized representative before entering subjects in this study: (1) a copy of the IRB/REB/IEC letter that grants formal approval; and (2) a copy of the IRB/REB/IEC-approved ICF.

10.3 Institutional Biosafety Committee (IBC) (where applicable)

This protocol and any accompanying material provided to the subject (such as subject information sheets, Informed Consent Form, or descriptions of the study used to obtain informed consent) will be submitted by BNI and/or the site to a legally constituted and chartered Institutional Biosafety Committee (IBC). Additional materials, such as the Investigator's Brochure, will be submitted to the IBC according to the specific Committee and federal (United States' National Institutes of Health or foreign equivalent) requirements. Each site will be approved by the IBC in accordance with local procedures and country-specific regulatory requirements. Documentation of IBC approval must be in place prior to drug shipment to the site.

At the discretion of the specific IBC and within federal requirements, IBC oversight of individual sites may be terminated provided (1) all subjects at that site have completed dosing by at least 28 days, and (2) all investigational materials have been fully accounted for and either returned to BNI, destroyed on site, or

shipped to a duly licensed destruction facility and a shipping and inventory reconciliation records have been filed in the Pharmacy Manual.

